Study Protocol Cover Page

Document Title: Study Protocol

Study Official Title: Evaluation of Osteopathic Treatment in Adults with Nonspecific Neck Pain

NCT Number:

Date of Document: 12 November 2024

Sponsor / Institution: Istanbul Rumeli University

Confidentiality Statement: This document contains confidential information. Participants' names or personal identifiers are **not included**.

Brief Description: This study protocol describes a randomized, parallel-group interventional study comparing osteopathic treatment plus standard physical therapy versus standard physical therapy alone in adults with nonspecific neck pain. The protocol includes study objectives, eligibility criteria, interventions, outcome measures, and assessment schedule. The participants pain intensity (VAS), functional status (NDI), quality of life (SF-36), muscle strength, and cervical range of motion.

Statistical Cover Page

Document Title: Statistical Analysis Plan

Study Official Title: Evaluation of Osteopathic Treatment in Adults with Nonspecific Neck Pain

NCT Number:

Date of Document: 12 November 2024

Sponsor / Institution: Istanbul Rumeli University

Confidentiality Statement: This document contains confidential information. Participants' names or personal identifiers are **not included**.

Brief Description: The Statistical Analysis Plan outlines the methods for analyzing the primary and secondary outcomes of the study, including pain intensity (measured using the Visual Analog Scale, VAS), functional status (assessed using the Neck Disability Index, NDI), quality of life (evaluated using the Short Form-36, SF-36), muscle strength, and cervical range of motion. The plan describes statistical tests, significance thresholds, handling of missing data, and subgroup analyses for the randomized, parallel-group design. The Shapiro–Wilk test will be used to test the normality of data distribution. A paired sample t-test and an independent sample t-test will be used. A p-value of less than 0.05 ($p < 0.05$) will be considered statistically significant for all analyses.

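### The only between-arm test named is an unadjusted independent t-test; unless the full SAP already adjusts for baseline, ANCOVA would usually be more precise at almost no cost

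*Combined protocol and SAP*

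**What the plan says.** The Brief Description on the Study Protocol Cover Page calls the trial a "randomized, parallel-group interventional study comparing osteopathic treatment plus standard physical therapy versus standard physical therapy alone". The outcomes are "pain intensity (VAS), functional status (NDI), quality of life (SF-36), muscle strength, and cervical range of motion", all continuous or scale measures.

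The Brief Description on the Statistical Cover Page gives the methods. After a normality check ("The Shapiro–Wilk test will be used to test the normality of data distribution") it states: "A paired sample t-test and an independent sample t-test will be used". A p-value below 0.05 "will be considered statistically significant for all analyses". It names no covariate, ANCOVA, regression or mixed model. It does not say whether the independent t-test is applied to follow-up or change scores, or which outcomes and times the paired test covers.

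Both texts are summaries of fuller documents. Of the protocol: "The protocol includes study objectives, eligibility criteria, interventions, outcome measures, and assessment schedule". Of the SAP: "The plan describes statistical tests, significance thresholds, handling of missing data, and subgroup analyses for the randomized, parallel-group design". That fuller content is not available here, and baseline adjustment is not among the topics listed.

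**The concern.** The trial's question is between arms. The paired t-test works within persons and cannot answer it, so the independent t-test has to. The paired test does imply, in a two-arm parallel trial, that at least some outcomes are measured before treatment, so a baseline covariate is probably already collected.

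For those outcomes the independent t-test either ignores the baseline (follow-up scores) or subtracts it with a fixed weight of 1 (change scores). ANCOVA estimates the weight from the data. Without it, the confidence interval for the treatment effect is usually wider than the same data allow, and a real effect is more likely to be missed. A chance baseline difference also stays in the estimate of that one trial.

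Leaving open which score is tested adds an analyst's choice that can itself move power materially.

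**Working it through.** **Inputs.** The two-arm parallel design, the two t-tests and the 0.05 threshold come from the two Brief Descriptions. The documents state no sample size, SD, effect size, allocation ratio or correlation, so there is no planned figure to reproduce. Assumptions: 20, 30 or 50 per arm, 1:1 allocation, normal data, two-sided testing, and rho (baseline to follow-up correlation) of 0.3, 0.5 or 0.7. Let k = baseline SD / follow-up SD and N = total sample size.

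**Variance factors, in units of follow-up variance**

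- t-test on follow-up scores: 1
- t-test on change scores: 1 + k² − 2·rho·k
- ANCOVA: (1 − rho²)(N − 3)/(N − 4), where the last ratio is the cost of estimating the slope

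In large samples ANCOVA's variance is lower by rho² than that of follow-up scores. Because 1 + k² − 2·rho·k = (1 − rho²) + (k − rho)², it is lower by (k − rho)² than that of change scores.

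| | rho 0.3 | rho 0.5 | rho 0.7 |
|---|---|---|---|
| ANCOVA, 20 per arm (×37/36) | 0.935 | 0.771 | 0.524 |
| ANCOVA, 30 per arm (×57/56) | 0.926 | 0.763 | 0.519 |
| ANCOVA, 50 per arm (×97/96) | 0.919 | 0.758 | 0.515 |
| Change, k = 1 | 1.40 | 1.00 | 0.60 |
| Change, k = 0.7 | 1.07 | 0.79 | 0.51 |

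**Extra participants for ANCOVA's precision** (ratio of factors minus 1, over 20 to 50 per arm; for example 1/0.771 − 1 = 30%)

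| | rho 0.3 | rho 0.5 | rho 0.7 |
|---|---|---|---|
| Follow-up t-test | 7-9% | 30-32% | 91-94% |
| Change t-test, k = 1 | 50-52% | 30-32% | 14-16% |
| Change t-test, k = 0.7 | 14-16% | 2-4% | −3 to −1% |

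**Power at 30 per arm.** Noncentral t, with the effect set so that the follow-up t-test has 80%. ANCOVA is averaged over chance imbalance, with N − 3 degrees of freedom.

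| | rho 0.3 | rho 0.5 | rho 0.7 |
|---|---|---|---|
| ANCOVA | 83% | 89% | 97% |
| Change, k = 1 | 66% | 80% | 95% |
| Change, k = 0.7 | 77% | 88% | 97.5% |

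**Where ANCOVA does not gain** (20 / 30 / 50 per arm)

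- Against follow-up scores: rho below √(1/(N − 3)) = 0.16 / 0.13 / 0.10.
- Against change scores: |k − rho| below √((1 − rho²)/(N − 4)). At rho = 0.5 this is 0.14 / 0.12 / 0.09. With k = 1 it means rho above (N − 5)/(N − 3) = 0.946 / 0.965 / 0.979.
- The worst loss inside these zones is 1/(N − 4) = 2.8% / 1.8% / 1.0% of variance. At 20 per arm and rho = 0, power is 79% instead of 80%. At k = rho = 0.5 the variance is 0.771 against 0.750 for change scores, and power is 89% against 90%.

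**Chance imbalance.** For a standardised baseline difference d, the estimate shifts by rho·d follow-up SDs with follow-up scores and by −(k − rho)·d with change scores.

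**Error rate.** In simulation under no effect (20,000 trials per setting, 20 and 30 per arm, seven rho-k pairs including no-gain cases), all three methods rejected in 4.6% to 5.3% of trials.

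**The case against.** The strongest objection is that the available text is two cover-page summaries. A one-sentence list of tests does not show that the full SAP lacks an adjusted model, and pre-treatment measurement is inferred from the paired test, not stated. This stands, and it is why the point is conditional. Nothing in the available text rebuts the point either.

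Second, the t-test is valid, so this is a preference for efficiency. That is also true. It limits how strongly the point can be put, but does not remove it: the remedy is cheap and the possible gain is large.

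Third, the gain over change scores depends on k. With k = 0.7 the saving falls to 2-4% at rho = 0.5 and turns slightly negative at rho = 0.7. This stands too. The case is secure against follow-up scores at moderate rho, and weaker against change scores when the baseline SD is the smaller one.

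Fourth, the cost rises in a very small trial: 1/(N − 4) is 3.8% at 15 per arm and 6.2% at 10. That is still modest beside the likely gain.

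Finally, the figures assume normal data although VAS and NDI are bounded, and a switch to ANCOVA leaves open what the Shapiro–Wilk test is applied to. The second matter is one of wording and can be settled in the same edit.

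**Conclusion.** The concern holds, on the condition that the full SAP does not already adjust for baseline. The only between-arm method in the available text is unadjusted. For outcomes with a baseline value, ANCOVA would usually give a more precise estimate from the same data. At rho = 0.5 the saving is about 30% in effective sample size against follow-up scores, or against change scores with k = 1. The most it can cost is 2.8% of variance at 20 per arm.

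The size of the gain in this trial cannot be computed, because sample size, rho, k and the score tested are all unstated. The planned test's error rate is not in question. This is a change that should be made, held with medium confidence.

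**What to change.** Unless the full SAP already adjusts for baseline (in which case the sponsor need only confirm it), state:

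> For each continuous outcome measured at baseline, the arms will be compared by ANCOVA of the value at [the prespecified follow-up time] on arm and the baseline value of the same score. The adjusted mean difference, its 95% CI and the p-value will be reported. The unadjusted independent t-test of the same follow-up value is a sensitivity analysis.

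Where an outcome yields several scores (SF-36 subscales, muscle groups, movement directions), fit one model per analysed score with its own baseline. An outcome without a baseline value keeps the independent t-test. Say also that normality is judged on the model residuals.

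**Cost.** No extra participants or visits for outcomes already measured at baseline. The SAP needs the model wording, plus the follow-up time and analysed score for each outcome. Statistically, the price is one degree of freedom and the small slope-estimation cost shown above.
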